## 6.7. Software Version

All analyses will be conducted using SAS version 9.4 or above.

# 7. STATISTICAL CONSIDERATIONS

## 7.1. Adjustments for Covariates and Factors to be Included in Analyses

The following factors and covariates will be used in the ANCOVA analyses: study intervention group (375\_B, 375\_A, 750\_B, 750\_A) as a fixed effect and the  $\log_{10}$ -transformed titer pre-dose 1 (Day 1) as a covariate. For details, refer to [15.1](#) and [15.2](#).

---

Document: \\ieedc-vnasc01\BIOSdata\GSK\H5N8(Flu)\HAB99808\Biostatistics\Documentation\SAP\SAP\SAP v5.0\GSK H5N8-219833\_SAP\_v5.0\_19AUG2024.docx

Author: PPD Version Number: 5.0

Version Date: 19AUG2024

Template No.: CS\_TP\_BS016 Revision 7

Reference: CS\_WI\_BS005

Effective Date: 01Nov2021

## 7.2. Multicenter Studies

This study will be conducted by multiple investigators at multiple centers within the United States (US). The participants will be randomized to one of the 4 groups (refer to 25) which will be performed in a 1:1:1:1 ratio prior to intervention to provide approximately 130 enrolled participants per study intervention group. No subgroup or adjustment is planned for study effect.

## 7.3. Missing Data

Missing data (missing, incomplete or partial dates, AE measurement [including missing AE severity and relationship], prior and concomitant medications and death date) will be handled as per [APPENDIX 2](#) of this SAP.

Missing immunogenicity data will not be imputed. Titers below LLOQ will be replaced by LLOQ/2 for the purpose of GMT computation. Titers above the ULOQ will be replaced by the ULOQ.

## 7.4. Multiple Comparisons/ Multiplicity

There are 2 primary endpoints to be accounted for in this study. Success will be achieved if the 2 criteria are met simultaneously:

- LL of the 95% CI for the SPR  $\geq$  70% for adults 18 to 64 years of age, AND
- LL of the 95% CI for the SPR  $\geq$  60% for adults  $\geq$  65 years of age.

No multiplicity adjustment is required as the hypothesis for each study group will be tested if the success criteria will be met for the previous group in the hierarchy. Accordingly, a nominal type I error of 2.5% will be used for each dose group and the objective will be met for one dose group if all 2 null hypotheses are rejected simultaneously.

## 7.5. Examination of Subgroups

All endpoints will be produced separately for each age group: 18 to 64 years of age and  $\geq$  65 years of age.

---

Document:	\ieedc-vnasc01\BIOSdata\GSK\H5N8(Flu)\HAB99808\Biostatistics\Documentation\SAP\SAP\SAP\SAP v5.0\GSK H5N8-219833_SAP_v5.0_19AUG2024.docx		
Author:	PPD	Version Number:	5.0
		Version Date:	19AUG2024

Template No.: CS\_TP\_BS016 Revision 7

Reference: CS\_WI\_BS005

Effective Date: 01Nov2021

## **8. OUTPUT PRESENTATIONS**

[APPENDIX 1](#) shows conventions for presentation of data in outputs.

The templates provided with this SAP describe the presentations for this study and therefore the format and content of the summary tables, figures, and listings to be provided by IQVIA Biostatistics. Statistical output numbering will follow 'ICH E3 Structure and Content of Clinical Study Reports'.

## **9. DISPOSITION AND WITHDRAWALS**

### **9.1. Disposition**

Participant disposition will be summarized for the enrolled set across groups and for ES for each study group and overall. Specifically, the number of participants enrolled but not exposed will be summarized with reason for no exposure. The number of exposed participants will be summarized to provide the number who completed study vaccinations, who discontinued vaccinations, who completed the study, who discontinued from the study with the reason for discontinuation.

### **9.2. Protocol Deviations**

Protocol deviations (PDs) will be collected in a PD log, as detailed in the PDMP. All PDs will be assessed as either important or non-important. PDs will be reviewed by the sponsor, and their status confirmed by the time that all data are cleaned for the Interim and Final Analyses. A summary table presenting the number and percentage of participants with important PDs (i.e., those PDs associated to elimination from PPS and DS), and the number and percentage of participants excluded from the PPS and DS analyses respectively will be presented for participants in the ES by study intervention and overall. A listing of all PDs including an indicator of those important, excluded from the ES, PPS and DS will be provided for the ENR.

## **10. DEMOGRAPHIC AND OTHER BASELINE CHARACTERISTICS**

Demographic data and other baseline characteristics will be presented for the ES and PP sets. The following demographic and other baseline characteristics will be reported for this study:

---

Document: \\ieedc-vnasc01\BIOSdata\GSK\H5N8(Flu)\HAB99808\Biostatistics\Documentation\SAP\SAP\SAP v5.0\GSK H5N8-219833\_SAP\_v5.0\_19AUG2024.docx

Author: PPD Version Number: 5.0

Version Date: 19AUG2024

Template No.: CS\_TP\_BS016 Revision 7

Reference: CS\_WI\_BS005

Effective Date: 01Nov2021

- Age (years) – at the time of first study intervention
- Age category (18-64 and  $\geq$  65 years of age)
- Sex
- Race (as per Clinical Data Interchange Standards Consortium [CDISC] categories)
- Ethnicity
- Center
- Occupation

Descriptive statistics (mean, median, standard deviation, and range) will be presented for continuous variables and frequency counts and percentages for categorical variables. A listing for demographic and other baseline characteristics will be provided for the ENR.

No statistical testing will be carried out for demographic or other baseline characteristics.

Pregnancy test results pre-vaccination will be presented in a listing, for the ENR.

## **11. GENERAL MEDICAL / VACCINATION HISTORY AND EXAMINATIONS**

Medical / Vaccination History information will be summarized for the ES.

- Medical History will be coded using Medical Dictionary for Regulatory Activities (MedDRA) central coding dictionary, Version 25.1 or higher.
- Data captured on the “Medical History” page of the eCRF will be presented by System Organ Class (SOC), High Level Terms (HLT) and Preferred Term (PT). Medical occurrences that begin before the start of study intervention but after obtaining informed consent will be recorded on the Medical History section of the eCRF, not the adverse events (AE) section. However, if medical occurrences are considered by the investigator to be related to study conduct, then this would be reported as an AE.

A listing of medical / vaccination history data will be provided.

---

Document: \\ieedc-vnasc01\BIOSdata\GSK\H5N8(Flu)\HAB99808\Biostatistics\Documentation\SAP\SAP\SAP v5.0\GSK H5N8-219833\_SAP\_v5.0\_19AUG2024.docx

Author: PPD Version Number: 5.0

Version Date: 19AUG2024

Template No.: CS\_TP\_BS016 Revision 7

Reference: CS\_WI\_BS005

Effective Date: 01Nov2021

## **12. PRIOR, CONCOMITANT AND CO-ADMINISTERED VACCINATIONS**

Prior, concomitant and co-administered vaccination will be coded with the current version of the World Health Organization Drug Dictionary (WHODD), summarized and listed, for the ES.

- Prior vaccinations are vaccinations given to participants prior to the dosing of first study intervention.
- Concomitant vaccinations are defined as any vaccine that the participant is receiving on or after the day of the first administration of study intervention.

## **13. MEDICATIONS**

Medications will be presented for the ES. The number and percentage of participants and doses using concomitant medication during the 21-day follow-up period (i.e., on the day of each vaccination and 20 subsequent days) will be summarized by study intervention group for each study intervention administration and overall will be summarized. Medications will be summarized using WHO ATC level 3 categories.

See [APPENDIX 2](#) for handling of partial dates for medications, in the case where it is not possible to define a medication as prior or concomitant, the medication will be classified by the worst case; i.e., concomitant.

Further details are in Section 6.8 of the Protocol. Concomitant medications that are taken within 21-days follow-up period post each vaccination will be presented in table summaries and in listings for all medications. Medications will be listed for the ES.

## **14. STUDY MEDICATION EXPOSURE**

Exposure to study intervention will be presented for the ES.

## **15. IMMUNOGENICITY OUTCOMES**

The primary analysis will be based on the PPS for analysis of immunogenicity. If, in any study intervention group, the percentage of vaccinated participants with serological results excluded from the PPS at one of the post intervention time points is 5% or more, a second analysis based on the ES will be performed to complement the PPS analysis.

A sensitivity analysis will also be performed on the primary endpoints, to evaluate the immunogenicity in subjects

---

Document: \\ieedc-vnasc01\BIOSdata\GSK\H5N8(Flu)\HAB99808\Biostatistics\Documentation\SAP\SAP\SAP v5.0\GSK H5N8-219833\_SAP\_v5.0\_19AUG2024.docx

Author: PPD Version Number: 5.0

Version Date: 19AUG2024

Template No.: CS\_TP\_BS016 Revision 7

Reference: CS\_WI\_BS005

Effective Date: 01Nov2021

who had Visit 3 and 5 performed within the study windows [14-28 days], as specified in Protocol version 1 amendment 2.

## 15.1. Primary Immunogenicity

### 15.1.1. Primary Immunogenicity Variables & Derivations

The primary immunogenicity endpoints are:

- Vaccine-homologous HI titers at Day 43 (GMTs)
- Vaccine-homologous HI titers increase at Day 43 compared to visit 1 (Geometric Mean Fold Rise [GMFR])
- Seroprotection (SP) defined as titer  $\geq 1:40$  at Day 43 (percentage of participants meeting SP criteria)

See [section 7.4](#) for details on the handling of multiple primary endpoints.

### 15.1.2. Intercurrent Event Handling and Data Imputation for Primary Immunogenicity Variables

Missing data will not be replaced. Refer also to PPS in section 5.6 and estimand section 2.4.

### 15.1.3. Primary Analysis of Primary Immunogenicity Variables

The primary immunogenicity endpoints will be analyzed, for the PPS, as follows:

- GMTs, with 95% CIs, will be calculated for each study intervention group for vaccine-homologous H5N8 HI titer at Day 43.
- GMFR at Day 43, compared to pre-vaccination, will be calculated for each study intervention group for vaccine-homologous H5N8 HI titer at Day 43 with 95% CIs.
- The CIs for GMT and GMFR and will be derived from an ANCOVA model on log-transformed titer. This model will include the dose group effect (i.e., 4 dose groups) as a fixed effect and the log-transformed titer pre-dose 1 (Day 1) as a covariate.
- HI SP, defined as meeting vaccine-homologous H5N8 HI titer  $\geq 1:40$ , will be analyzed by reporting SPR.

---

Document: \\ieedc-vnasc01\BIOSdata\GSK\H5N8(Flu)\HAB99808\Biostatistics\Documentation\SAP\SAP\SAP v5.0\GSK H5N8-219833\_SAP\_v5.0\_19AUG2024.docx

Author: PPD Version Number: 5.0  
Version Date: 19AUG2024

Template No.: CS\_TP\_BS016 Revision 7

Reference: CS\_WI\_BS005

Effective Date: 01Nov2021

SPR is defined as the percentage of participants who meet the SP definition and will be reported at Day 43 with Clopper-Pearson exact two-sided 95% CIs for each study intervention group.

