6.3 Measures to Minimize Bias: Randomization and Blinding

All participants will be centrally assigned to randomized study intervention using an interactive web response system (IWRS). The randomization will be stratified by age subgroup and use a permutation blocking scheme. Before the study is initiated, the log-in information and directions for the IWRS will be provided to each study site.

Data will be collected in an observer-blind manner. The investigator(s), their staff and the participants will not be aware of the study intervention assignment. The study intervention will be prepared and administered by qualified study personnel who can be aware of the intervention assignment. The number of each intervention kit will be recorded in the eCRF.

The laboratory in charge of sample testing will be blinded to the study intervention assignment. Codes will be used to link the participant and study to each sample. There will be no link between the study intervention and the identity of the participant.

GSKs Global Safety staff may unblind the intervention assignment for any participant with an SAE. If the SAE requires that an expedited regulatory report be sent to one or more regulatory agencies, a copy of the report, identifying the participant's intervention assignment, may be sent to investigators in accordance with local regulations and/or GSK policy.

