9.2 Sample Size Determination

A total of 520 participants are planned to be enrolled, with 65 participants per age subgroup in each of the 4 dose groups.

A non-evaluable rate of 23% and 30% in 18 to 64 years of age and ≥ 65 years of age groups, respectively yield an approximate sample size of 95 evaluable participants per dose group (i.e., 50 participants between 18 to 64 years of age and 45 participants above 65 years of age in each dose group), giving 77.8% overall power to fulfill the 2 SPR immunogenicity criteria in any in the first group that is 7.5 mcg antigen + AS03A. This assumes that the SPR are truly 20% higher than the critical value (namely 90% for participants 18 to 64 years of age and 80% for participants ≥ 65 years of age, respectively).

The statistical power in 7.5 mcg antigen + AS03A group will be 91.4% if the SPR is assumed as 85% in ≥ 65 years of age.

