9.4.3 Primary Endpoint(s)/Estimand(s) Analysis

9.4.3.1 Immunogenicity

Primary immunogenicity analyses will be based on the PPS.

GMTs and associated 95% CI will be calculated for each study group for vaccine-homologous H5N8 HI titer at Day 43.

GMFR increase at Day 43, compared to pre-vaccination and associated 95% CI will be calculated for each study group for vaccine-homologous H5N8 HI titer at Day 43. The GMT and GMFR CIs will be derived from an Analysis of Covariance (ANCOVA) model on log-transformed titer. The model will include the dose group effect (i.e., 4 dose groups), as a fixed effect and the log-transformed titer pre-dose 1 (Day 1) as a covariate.

SPR at Day 43 will be calculated for each study group for vaccine-homologous H5N8 HI titer along with Clopper-Pearson exact two-sided 98.75% CIs.

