## 6. GENERAL CONSIDERATIONS

Data will be summarized descriptively (frequency and percentage for categorical data and mean, standard deviation [SD] and range for continuous data, unless specified otherwise). In summary tables for categorical data for which categories are defined on the eCRF, all categories will be presented as specified, even if the participants count within that category is zero. All analyses will be provided separately for each age groups 18 to 64 years of age and for 65 years of age or above.

Unless otherwise specified, all data collected during the trial will be presented in listings for the ENR.

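### Adding age in years to the primary GMT/GMFR ANCOVA would probably narrow the 18-64 intervals slightly; it would do almost nothing in the older stratum and would not touch the SPR decision

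*SAP*

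**What the plan says.** SAP 15.1.3 takes the confidence intervals for Day 43 GMT and GMFR from an ANCOVA on log titer with "the dose group effect (i.e., 4 dose groups) as a fixed effect and the log-transformed titer pre-dose 1 (Day 1) as a covariate". SAP 7.1, which opens "The following factors and covariates will be used in the ANCOVA analyses", lists only those two terms, and the estimand table in SAP 2.4 repeats them. Protocol 9.4.3.1 has the same model: "The model will include the dose group effect (i.e., 4 dose groups), as a fixed effect", plus the Day 1 titer. Protocol 9.4.4.1 and SAP 15.2.3 use it for the secondary post-vaccination HI titers.

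Age enters in two other ways. Protocol 6.3 says "The randomization will be stratified by age subgroup", and SAP 6 says "All analyses will be provided separately for each age groups 18 to 64 years of age and for 65 years of age or above". SAP 7.2 gives the allocation as "performed in a 1:1:1:1 ratio prior to intervention". SAP 10 reports age in years "at the time of first study intervention" as a baseline characteristic.

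GMT and GMFR are named primary endpoints (SAP 15.1.1). The hypotheses, success criteria and sample size (Protocol 9.1 and 9.2; SAP 2.3, 2.5 and 7.4) concern the SPR only, with Clopper-Pearson intervals in SAP 15.1.3.

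**The concern.** Within the 18-64 stratum the model treats people 46 years apart in age as exchangeable once Day 1 titer is known. If Day 43 titer varies with age inside the stratum, that variation stays in the residual and widens every GMT and GMFR interval. Nothing in the design balances age in years between dose groups within a stratum. A chance difference in mean age therefore passes into the comparison of formulations, which Protocol 4.2 gives as a purpose of the design, and into the adjusted GMT ratio described in SAP 6.5.

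The one planned covariate may also do little. If most Day 1 titers are below the LLOQ, it is nearly constant. That is an assumption: Protocol 2.1 calls human infection unlikely at present, but Protocol 10.1.5 intends to recruit poultry workers.

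At stake is modest precision on endpoints reported as primary, in about 50 evaluable participants per dose group in 18-64 and 45 in ≥65.

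**Working it through.** **The plan's own figure.** With 50 and 45 evaluable (65 × 0.77 = 50.05; 65 × 0.70 = 45.5), the smallest counts whose 95% Clopper-Pearson lower limit reaches 70% and 60% are 42/50 and 34/45. Exact power is 0.942 at a true SPR of 90% and 0.826 at 80%, and 0.942 × 0.826 = 77.8%. With 85% in ≥65 it is 0.942 × 0.970 = 91.4%. Both stated powers reproduce. No covariate enters them, so an age term leaves them unchanged.

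**Effect of an age term.** The documents give no titer SD and no age-titer correlation. Let r be the correlation of age with log Day 43 titer within a stratum, given dose group and Day 1 titer. With N participants over four equal groups, the expected ratio of log-scale interval widths for a group mean, with versus without age, is

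sqrt[(1 − r²) × (1 + 0.75/(N − 6))] × t(0.975, N − 6)/t(0.975, N − 5).

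For 18-64, N = 4 × 50 = 200 and the t ratio is 1.00003. For ≥65, N = 4 × 45 = 180 and it is 1.00004.

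| r (assumed) | Width change, 18-64 | Width change, ≥65 |
|---|---|---|
| 0 | +0.2% | +0.2% |
| 0.1 | −0.3% | −0.3% |
| 0.2 | −1.8% | −1.8% |
| 0.3 | −4.4% | −4.4% |

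Break-even is at r of about 0.06 in 18-64 and 0.07 in ≥65. A simulation for 18-64 (4,000 runs per value, age uniform over the stratum) gave the same average changes. The interval narrowed in 23% of cases at r = 0, 56% at 0.1, 93% at 0.2 and 99.9% at 0.3.

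**A rough range for r.** The only handle in the plan is its pair of assumed SPRs. Read as a shift in a normal log titer, 90% versus 80% is 1.282 − 0.842 = 0.44 SD; with the 85% alternative it is 1.282 − 1.036 = 0.245 SD. Assume the stratum mean ages differ by 27-31 years, the age SD is 12-13.4 years in 18-64 and 5-6 in ≥65, and the slope is linear. Then r = (shift / years between means) × age SD:

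| Stratum | SPR pair | r | Net width change |
|---|---|---|---|
| 18-64 | 90/80 | 0.44/31 × 12 = 0.17 to 0.44/27 × 13.4 = 0.22 | −1.3% to −2.2% |
| 18-64 | 90/85 | 0.245/31 × 12 = 0.095 to 0.245/27 × 13.4 = 0.12 | −0.3% to −0.6% |
| ≥65 | 90/80 | 0.44/31 × 5 = 0.07 to 0.44/27 × 6 = 0.10 | 0.0% to −0.3% |
| ≥65 | 90/85 | 0.245/31 × 5 = 0.04 to 0.245/27 × 6 = 0.05 | about +0.1% |

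In participants, 50 × (1/width ratio² − 1) for 18-64 gives about 0.3 at −0.3% and 2.3 at −2.2%.

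**On the titer scale.** At an assumed SD of 0.6 log10, the 18-64 GMT interval is the estimate multiplied and divided by 1.470 without age. With age the factor is 1.471 at r = 0, 1.460 at r = 0.2 and 1.445 at r = 0.3.

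**Chance imbalance.** With an age SD of 12-13.4, the standard error of the difference in mean age between two groups of 50 is SD × sqrt(2/50) = 2.4-2.7 years, or 0.2 age SD. At r = 0.2, an imbalance of that size moves the comparison by 0.2 × 0.2 = 0.04 titer SD.

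**The case against.** The strongest reply is that nothing here is wrong. The model is prespecified in both documents, age is already handled by stratified randomization and separate analyses, and a further term is a matter of preference. That stands as far as error goes: omitting age is a legitimate choice.

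A reader might infer that the plan itself expects response to fall with age, since it assumes "namely 90% for participants 18 to 64 years of age and 80% for participants" in the older stratum. The documents do not support that. Protocol 9.2 and SAP 2.5 obtain both values by adding 20 points to thresholds of 70% and 60%. They are power assumptions, not an estimated age effect, and the same sections offer 85% as an alternative. The derived range for r is therefore only indicative.

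A reader might also infer that the change would help the trial meet its objective, or that narrower intervals are assured. Neither follows. No hypothesis or threshold attaches to GMT or GMFR, and the sign of the effect depends on an unknown correlation.

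Timing is a fair objection too. SAP v5.0 is dated 19 August 2024. Protocol 9.5 provides treatment-level unblinded Day 43 summaries to the sponsor and BARDA, and the documents do not say whether these had been released by then. A covariate added to the primary model after such results are seen would not be credibly prespecified. This limits the form of the fix but leaves the point standing.

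The gain itself survives: it is small and probable in 18-64, against a worst expected loss of about 0.2% of interval width.

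**Conclusion.** The point holds as an optional precision refinement of low importance. In 18-64, age adjustment would probably narrow the GMT and GMFR intervals by about 0.3-2.2% net if the within-stratum correlation is about 0.10-0.22, and by 4.4% if it is 0.3. It would also correct chance age imbalance between dose groups. In ≥65 the expected change is essentially nil (−0.3% to +0.1%). The correlation range rests on assumed mean ages, age SDs, a linear slope and SPR values chosen for power, so confidence in the size is low. The SPR decision rule, type I error and the 77.8% and 91.4% power figures are unaffected.

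**What to change.** If treatment-level immunogenicity results are still unseen, add age in years at first dose as a continuous covariate to the post-vaccination ANCOVA within each stratum, with least-squares means at the stratum's mean age. Make the change together in Protocol 9.4.3.1 and 9.4.4.1 and in SAP 2.4 (estimand table), 7.1, 15.1.3 and 15.2.3. Leaving out the estimand table would make the SAP contradict itself.

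If those results have been seen, keep the planned model as primary and report the age-adjusted model as a labelled supportive analysis. SAP v5.0 already added a sensitivity analysis on the primary endpoints in Section 15, so there is a natural place for it. SAP 3.3, which states no changes from the protocol, would then need a line.

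The cost is one residual degree of freedom (195 to 194 in 18-64), intervals up to about 0.2% wider if age is unrelated to titer, and a coordinated document update, which for the primary model means a protocol amendment. No new data are needed.

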## **15.2. Secondary Immunogenicity**

### **15.2.1. Secondary Immunogenicity Variables & Derivations**

The secondary immunogenicity endpoints are:

- Vaccine-homologous H5N8 HI titers at Day 1, 22, and 6 months post dose 2 (GMT).
- Vaccine-homologous N5N8 HI titers increase from pre-vaccination at Day 22, and 6 months post dose 2 (GMFR)
- SP, defined as titer  $\geq 1:40$  at Day 1, 22, and 6 months post dose 2 (percentage of participants meeting SP criteria)
- HI seroconversion (SC, defined as titer  $\geq 1:40$  for participants with pre-vaccination titer below 1:10 or as  $\geq 4$ -fold increase from pre-vaccination titer to Day 1, 22, 43 and 6 months post dose 2 for participants with pre-vaccination titer  $\geq 1.10$  (percentage of participants meeting SC criteria).
- Vaccine-homologous H5N8 MN titers at Day 1, 22, 43, and 6 months post dose 2 (GMT)
- Seropositivity rates defined as percentage of participants with reciprocal titer greater than or equal to the LLOQ at Days 1, 22, 43, and 6 months post dose 2 (percentage of seropositive participants)
- MN vaccine response (VR) defined as titer  $\geq 4 \times$  LLOQ for participants with pre-vaccination titer below LLOQ or a  $\geq 4$ -fold increase in titer for participants with pre-vaccination titer  $\geq$  LLOQ at Days 22, 43, and 6 months post dose 2 (percentage of participants meeting VR criteria). Neutralization titers below the LLOQ of the assay are given an arbitrary value of half the LLOQ for the purpose of vaccine response calculation.

